#### Primary and secondary endpoints

Primary endpoint: Comparing mesial-distal (M-D) bone loss between the two groups (Radiologic outcome)

Secondary endpoints: Clinical outcomes and Patient reporting outcomes

- 1. Determine the survival rate and success rate of the Group Short (GS) and Group Long (GL) group.
- 2. Compare incidence and types of surgical and prosthetic complications between groups
- 3. Compare the number of sites with bleeding on probing (BOP)
- 4. Compare the cost of both procedures and the cost of the prosthetic complications
- 5. Compare the probing pocket depth (PPD)
- 6. Determine the pain after treatment: Visual analog score (VAS)
- 7. Compare patient satisfaction
- 8. Compare surgical time

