#### **STUDY PROCEDURES**

#### **Clinical measurements**

1) The following measurements will be taken for each treated implant by a blinded, calibrated examiner at the implant placement (surgery V2), at the time of prosthetic placement (5-month postop V6), 12-month follow-up (V8), and 24-month follow-up (V10).

- Marginal bone level (MBL): It will be calculated based on standardized radiographs using registered bite-block with a Rinn (Dentsply Rinn, Elgin, IL, USA) film holder and expressed as the distance from the implant shoulder to the most coronal bone-to-implant contact (BIC) on the mesial and distal side of the implant. The mean values will be calculated for each implant at the time of implant placement, at the time of prosthetic placement (5-month post-op V6), 12-month follow-up (V8), and at 24-month follow-up (V10). In the case that the bone levels around the study implants are hidden or difficult to read, new radiographs will be taken. Peri-implant marginal bone levels will be measured using the ImageJ software\* (ImageJ, U. S. National Institutes of Health, Bethesda, Maryland, USA) (Schneider et al., 2012). The software will be calibrated for every single image using the known implant length or the length of the implant collar. Measurements of the mesial and distal bone crest level adjacent to each implant will be rounded to the nearest 0.1 mm. Implants with bone up to the coronal margin of the implant collar will be given a value of zero. Mesial and distal measurements of each implant are averaged, and a mean calculated at patient level and then at group level.
- PPD and BOP: It will be assessed at 4 sites per implant (mesial, distal, buccal, and palatal) with a measurement stent using a periodontal probe (UNC, Hu-Friedy, Chicago, IL, USA). PPD are measured from the distance of the mucosal margin to the bottom of the probable pocket in mm. BOP is recorded using the following scoring method: 0) no bleeding 1) an isolated bleeding spot is visible, 2) blood forms a confluent red line on margin, and 3) heavy or profuse bleeding.
- Plaque: The level of oral hygiene will be evaluated using the Modified gingival index (Lobene et al., 1986) (Scores 1-4).

0 = Absence of inflammation

1 = Mild inflammation or with slight changes in color and texture but not in all portions of gingival marginal or papillary

2 = Mild inflammation, such as the preceding criteria, in all portions of gingival marginal or papillary

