3 = Moderate, bright surface inflammation, erythema, edema and/or hypertrophy of gingival marginal or papillary

4 = Severe inflammation: erythema, edema and/or marginal gingival hypertrophy of the unit or spontaneous bleeding, papillary, congestion or ulceration.

- Prosthesis failure: Planned prosthesis which could not be placed due to implant failure(s), loss of the prosthesis secondary to implant failure(s), or replacement of the definitive prosthesis for any reason.
- Implant failure: It will be defined as implant mobility (assessed from force applied with two hand instrument), pain, or neuropathy.
- Implant success: It will be defined as 1) Absence of persistent subjective complaints such as pain, foreign body sensation and/or dysesthesia 2) Absence of a peri-implant infection with suppuration 3) Absence of mobility 4) Absence of a continuous radiolucency around the implant and 5) Absence of any biological or prosthetic complications (Buser et al., 2012)
- Peri-implantitis: It will be defined as detectable radiographic bone loss beyond the initial biological bone remodeling.

2) The following measurements will be taken for each treated implant by a blinded, calibrated examiner after implant placement, 12-month follow-up, and 24-month follow-up.

Bone thickness (BT): It will be determined based on CBCT and expressed as the distance from the most coronal bone-implant contact to the outer surface of the buccal plate. The mean values will be calculated for each implant.

3) The following measurements will be taken for each treated implant by a blinded, calibrated examiner at prosthetic placement, 12-month follow-up, and 24-month follow-up.

- Crown to implant ratio: The height of the crowns will be measured on the radiographs from the implant-abutment interface to the most coronal point on the crown. The anatomical crown-to-implant ratio (anatomical C/I ratio) will then be calculated dividing the anatomical crown by the length of the implant.4)
- 4) ISQ (Implant stability quotiant) will be measured at the time of healing abutment placement.

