#### **Screening & Pre-surgical procedures**

The medical history and vitals (heart rate and blood pressure) will be taken. In addition, clinical photographs and one standardized periapical radiograph will be completed. A CBCT scan will be taken before implant placement for screening eligibility, and impressions will be taken for surgical guide preparation. The CBCT scan may be scheduled separately due to availability of the CBCT machine.

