#### Risks associated with dental x-rays

In this study, patients will have about eight standard dental x-rays and two CBCT scans. They should experience no more discomfort related to the x-rays than they would with x-rays taken during regular dental visits. The only discomfort may be related to the x-ray film or film holder pressing on the soft tissues.

The biologic effect of radiation is termed "effective dose" (EF) and is expressed in milliSieverts (mSv). The amount of radiation for one dental x-ray is about 0.005 mSv and 5.3mSv for CBCT scan. This is considered to be a very small risk. The average radiation exposure that includes the natural background radiation an individual receives is about 3.1 mSv per year and about 0.008 mSv per day. The total amount of radiation exposure to patients from this study is minimal.

The researchers will try to minimize these risks by providing a lead apron that will be mandatory to wear during x-rays.

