## Appendix A: Schedule of Events Table

				1						
Visit	Screening & Pre- Surgical Visit (V1)	Surgery (V2)	2 weeks post-op (V3)	4 months post-op (V4)	4 months post-op (V5)	5 months post-op (V6)	5 months post-op (V7)	6 months post-crown delivery (V8)	12 months post-crown delivery (V9)	18 months post-crown delivery (V10)
Window		Baseline (BL)	± 2 days	$\pm 1$ month	2 weeks after V4 ± 2 days	$\pm 1$ month	$\pm 1$ month	$\pm 1$ month	$\pm 1$ month	$\pm 1$ month
Informed consent										
(*Inclusion & exclusion criteria)	*Х									
Medical History	Х	Х	Х	Х	Х	Х	Х	Х	Х	Х
Adverse Events		Х	Х	Х	Х	Х	Х	Х	Х	Х
CBCT scan (*May be scheduled separately)	*X									Х
Vitals (blood pressure & heart rate)	Х	Х								
Maintenance							Х	Х	Х	Х
Implant crown placement (definitive)							Х			
Radiograph (*Standardized)	*Х	X and *X		*Х			*X	*Х		*X
Suture removal			Х		Х					
Impression	Х					Х				
Photographs	Х	Х	Х	Х	Х		Х	Х		Х
Clinical measurement		Х		Х			Х	X		Х
Subject pain assessment			Х							
Patient satisfaction			Х					Х		Х

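### Buccal bone thickness is read at a contact point that shifts apically as buccal bone is lost, so at V10 implants are compared at different heights and a plate missing at the shoulder is not scored as zero.

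*Combined protocol and SAP*

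**What the plan says.** Clinical measurements, item 2, defines buccal bone thickness on CBCT as a distance "expressed as the distance from the most coronal bone-implant contact to the outer surface of the buccal plate". It fixes no height along the implant, names no slice, and gives no rule for a site with no buccal bone at the shoulder. The measurement is to be made "by a blinded, calibrated examiner after implant placement, 12-month follow-up, and 24-month follow-up", which is three times per implant.

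Item 1 of the same section uses a similar point for marginal bone level, defined as "the distance from the implant shoulder to the most coronal bone-to-implant contact (BIC"). That measure is mesial and distal, and is read on standardized film-holder radiographs.

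On imaging, Screening & Pre-surgical procedures says "A CBCT scan will be taken before implant placement for screening eligibility". Risks associated with dental x-rays says "patients will have about eight standard dental x-rays and two CBCT scans". The CBCT row of Appendix A is marked at V1 (screening) and V10 (18 months after crown delivery) only.

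The section on primary and secondary endpoints gives one primary, "Primary endpoint: Comparing mesial-distal (M-D) bone loss between the two groups (Radiologic outcome"), and eight secondary items. None of the nine is bone thickness or any other CBCT measure. Statistical Considerations has no analysis specific to bone thickness; it applies repeated-measures ANOVA to the parameters in general.

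**The concern.** A thickness comparison between arms needs both arms read at the same place. Here the place is set by where bone contact begins, and that point moves apically along the implant as buccal bone is lost. Implants with different amounts of buccal loss are therefore read at different levels of the ridge, so any difference in thickness mixes plate thickness with reading height.

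The rule also cannot register the event that a thickness measure should show most clearly. Where the buccal plate has gone at the shoulder, the reading is taken further along, where bone remains, and a positive number is recorded.

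At stake is the meaning of a between-arm difference in buccal thickness at V10. The listed endpoints are not at stake. A further question is what the V10 scan is for, since bone thickness is the only measurement described that uses a CBCT taken after implant placement.

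**Working it through.** **1. Scan count.** Appendix A marks CBCT at V1 and V10, which is 2 and agrees with the two scans in the x-ray risk section. The V1 scan precedes the implant, so it contains no bone-implant contact and cannot yield this measurement. That leaves one thickness reading per implant, at V10. Item 2 asks for three post-implant readings; with screening, that would need 3 + 1 = 4 scans. The sections disagree.

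**2. What the schedule allows.** With one reading per implant, no within-implant change can be computed and repeated-measures ANOVA cannot be applied to thickness. Only the between-arm comparison at V10 remains.

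**3. Shift in the reading.** Let h be the buccal bone height lost, θ the angle of the outer buccal wall to the implant axis (positive if the ridge widens apically), and t any true loss from the outer plate. Then

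change in reading = h × tan(θ) − t.

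Neither θ nor buccal h is in the documents. I assume h = 0.5 mm, borrowing the difference in bone loss that Statistical Considerations gives for powering the study; applying it to the buccal side is itself an assumption. I vary θ and set t = 0.

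| Assumed wall | h × tan(θ), h = 0.5 mm | h = 1.0 mm |
|---|---|---|
| 10° undercut | −0.088 mm | −0.176 mm |
| Parallel | 0 | 0 |
| 10° flare | +0.088 mm | +0.176 mm |
| 20° flare | +0.182 mm | +0.364 mm |
| 30° flare | +0.289 mm | +0.577 mm |

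For scale, both implants are 5.0 mm in diameter and the minimum ridge width is 7 mm. If the implant is centred, the buccal wall is (7 − 5)/2 = 1.0 mm at that minimum, so +0.09 to +0.29 mm is about 9 to 29% of it.

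**4. Absent plate, with no flare.** Take two implants with a parallel 1.0 mm buccal wall, one intact and one that has lost 0.5 mm of buccal bone height. Under the stated rule both read 1.0 mm. Read at the shoulder (0 mm), the intact one scores 1.0 mm and the other 0; at 1 mm from the shoulder both score 1.0 mm. The rule hides the difference even when the geometric shift is zero.

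**5. Exposure on the protocol's own figures.** 8 × 0.005 + 2 × 5.3 = 0.04 + 10.6 = 10.64 mSv. The V10 scan is 5.3 of this: 5.3/10.64 = 49.8%. Four CBCTs would give 0.04 + 4 × 5.3 = 21.24 mSv.

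**The case against.** The strongest reply has three parts.

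- **Thickness at the crest is a describable quantity.** It can be reported beside marginal bone level. That is true, and it would be too strong to say that the measure has no interpretation. It remains a different quantity from plate thickness at a common level, and the plan does not say that thickness at the crest is what it wants to compare.
- **The consequence is small.** No listed endpoint uses bone thickness, and a shift of 0.09 to 0.18 mm is close to the 0.1 mm rounding used for marginal bone level. This stands and limits the weight of the point. It does not answer the absent-plate problem, which needs no assumption about slope.
- **The objectives refer to radiological parameters in general**, so an unlisted radiographic measure is not outside the study's purpose. This also stands: the absence from the endpoint list is a listing gap.

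A reader might also infer four stronger things that the documents do not support:

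- That bone loss will make the plate look thicker. This needs a ridge that widens apically, which the documents do not describe; a parallel wall gives no shift, an undercut reverses it, and true outer-plate loss offsets it.
- That change between visits is distorted. Under Appendix A no such change can be computed. The problem would arise only if more post-implant scans were scheduled.
- That the primary endpoint is contaminated. It is mesial-distal and read on periapical films, not at the buccal contact on CBCT.
- That the V10 scan is pointless. Its purpose is not stated, and that it serves bone thickness is an inference from its only described use.

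**Conclusion.** The point holds as a defect in the reading rule for an unlisted measure. At V10, implants with more buccal bone loss are read at a more apical level, and a plate missing at the shoulder receives a positive value. Both consequences follow from the definition alone.

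The numerical shift is conditional: between about −0.09 and +0.29 mm for 0.5 mm of assumed buccal loss and wall angles from a 10 degree undercut to a 30 degree flare, before any true outer-plate loss. Neither the direction nor the size of a bias between arms can be established from the documents.

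Two linked gaps are matters of fact. Item 2 asks for three post-implant thickness readings while Appendix A and the x-ray risk section provide for one post-implant CBCT. And the only described use of the V10 scan, about half of the stated study exposure, is a measure that is not among the endpoints.

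**What to change.** In Clinical measurements, item 2, replace the reading level with fixed distances from the implant shoulder, for example 0, 1 and 3 mm, all of which lie within both the 5 mm and the 10 mm implant. Specify one CBCT slice for all levels, score zero where no buccal bone is present, and report the arm difference at each level as exploratory. This removes the h × tan(θ) term and lets plate loss at the shoulder show. The cost is a change of wording, a few more readings per existing scan, and some extra unadjusted comparisons, which the exploratory label should make plain.

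In the same edit:

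- Reconcile the three thickness time points in item 2 with the two CBCTs in the x-ray risk section and Appendix A, only one of which follows implant placement. If only one post-implant reading remains, say that thickness will be compared between arms at that visit and not as a change over time.
- Either add bone thickness to the endpoint list as secondary or exploratory, or state the purpose of the V10 CBCT. Whether the scan is worth its 5.3 mSv is the sponsor's judgement, but the protocol should give the reason.

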#### Intra-operatory measurements

- Subjective evaluation of the bone type (Lekholm & Zarb 1985) during implant site preparation will be performed by the surgeon.
  - Type 1: Almost entirely comprised of homogeneous compact bone

- Type 2: thick layer of compact bone surrounding a core of dense trabecular bone
- Type 3: thin layer of cortical bone surrounding a core of dense trabecular bone
- Type 4: Thin layer of cortical bone surrounding a core of low-density trabecular bone coupled with the surgeon's tactile perception
- Thickness of soft tissues will be measured with a 1.0-mm marked periodontal probe (UNC, Hu-Friedy, Chicago, IL, USA) on the top of bone crest in the center of future implant placement. This will ensure direct visibility of mucosal thickness during measurement.
- Patient phenotype: Classification of the patient's phenotype will be thin, medium, thick, or very thick by using the Colorvue biotype probe (Hu-Friedy).
- Chair time of the surgical procedure will be recorded from the end of local anesthesia until the completion of sutures.
- The time required for placement of one single implant, with both treatments (short implants and sinus floor elevation with placement of longer implants) will be calculated as follows: the time required for the entire surgical procedure (from anesthesia to sutures) will be assessed for each patient and divided by the number of installed fixtures. The ratio of the time required for placement of a single short implant to the time required for a sinus floor elevation procedure in combination with a longer implant will be calculated and expressed as a percentage.
- A wireless magnetic-based Osstell Mentor RF Analyzer (Ostell USA, Linthicum, MD, USA) will be used to assess primary implant stability. The designated transducer (SmartPeg) will be hand-tightened per the manufacturer's instructions to the fixture. ISQ values will be taken immediately after implant placement and measured in triplicate and averaged to yield the mean baseline ISQ value for each implant.

## Clinical measurement to monitor early healing

 At the 2-week post-op suture removal visit (± 2 days after surgery) clinical photographs will be taken. In addition, data on soft tissue complications (edema, bleeding), general discomfort, pain (measured by VAS from 0 to 100) (Appendix A) and patient satisfaction (Appendix B) will also be collected at the 2-week post-op visit.

## Demographic data and patient questionnaires

At the pre-surgical visit, age, gender, smoking habits (number of cigarettes/day) will be recorded.

At the 2-week post-op visit, data on post-operative pain during the first day and possible side

effects or complications of the first three days will be registered. Patient discomfort will be measured by VAS scale and number of post-operative pain medication quantified. Patients will receive 3 sheets containing the VAS scale to be filled out daily. In case of drop out, the related reason will be registered (Appendix B).

Furthermore, all patients will be asked at the 2-weeks, 12-month, and 24-month follow-up to give their perception of the received therapy by completing a questionnaire concerning function, esthetics, cleaning of the implant-supported restorations, satisfaction, and cost (Appendix C).

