#### Participants

50 patients satisfying the following inclusion criteria will be recruited:

- Age 20 years or older at enrollment
- Able to provide informed consent
- Systemically healthy patients

- Full-mouth plaque score and full-mouth bleeding score ≤ 30% (measured at four sites per tooth)
- Missing one premolar, 1st molar, or 2nd molar in the maxillary arch (Minimum healing time after extraction: ≥4 months)
- One neighboring tooth or implant restoration must be present to the implant site.
- Presence of natural tooth/teeth, partial prosthesis and/or implants in the opposite jaw in contact with the planned crown/s deemed by the investigator as likely to present an initially stable implant situation
- Residual bone height under the maxillary sinus more than 5 mm but less than 8 mm and a width of at least 7 mm, as measured on cone beam computer tomography (CBCT) scans.

Exclusion criteria are:

- Unlikely to be able to comply with study procedures
- Uncontrolled pathologic processes in the oral cavity
- History of allergic reactions to dental local anesthetics
- History of head and neck chemotherapy or radiation within 5 years prior to surgery
- Systemic or local disease or condition that could compromise post-operative healing and/or osseointegration, such as HIV infection, Paget's disease, osteoporosis, etc.
- Uncontrolled diabetes mellitus (HbA1c >8)
- Patients taking corticosteroids, IV bisphosphonates, or any other medication that could influence post-operative healing and/or osseointegration
- Smokes more than 10 cigarettes/day
- Present alcohol and/or drug abuser (self-reported)
- Pregnant, unsure pregnancy status, or lactating females (self-reported), or planning to become pregnant within 1 year of study enrollment
- Any medical conditions that may affect the outcome of the study.

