#### STATISTICAL CONSIDERATIONS

The study will be powered to detect a minimum clinically significant difference in bone loss of 0.5 mm using  $\alpha = 0.05$ , a power  $(1 - \beta) = 80\%$ . Considering possible dropouts, the number of patients will also be increased by 10% for each arm. On the basis of this data, the minimum needed number of patients to be enrolled in this study is 17 with for the test group (GS) and 17 for the control group (GL). Mean values, standard deviations, and medians will be calculated for the clinical parameters. The association between crown-implant ratio and final bone loss as well as prosthetic complications will be examined. Changes of the parameters over time within the two groups as well as differences between groups will be analyzed using repeated measure of analysis of variance (ANOVA).

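### The primary comparison of bone loss names no pre-allocation covariate, so any precision that cigarettes/day or CBCT bone height could add goes unused

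*Combined protocol and SAP*

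**What the plan says.** The primary endpoint is "Comparing mesial-distal (M-D) bone loss between the two groups (Radiologic outcome"). No time point and no covariate are attached to it.

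The analysis text is a few lines in Statistical Considerations. Changes over time and differences between groups "will be analyzed using repeated measure of analysis of variance (ANOVA"). No adjusted model appears. The only association planned is between crown-implant ratio and final bone loss or prosthetic complications.

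Randomization and masking of examiners describes a computer-generated list. It states no stratification or minimisation factor, and says that concealment is broken after the flap is reflected.

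Two site or patient characteristics that could serve as covariates are obtained before that moment:
- Smoking. Under Demographic data and patient questionnaires, "age, gender, smoking habits (number of cigarettes/day) will be recorded" at the pre-surgical visit. Smokers of up to 10 cigarettes/day remain eligible.
- Bone height. Eligibility requires "Residual bone height under the maxillary sinus more than 5 mm but less than 8 mm", measured on CBCT.

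Marginal bone level (MBL) is first measured at implant placement (V2) and then at later visits.

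**The concern.** This is a small trial. The stated minimum is 17 per arm and the ceiling is 50 patients in all. A baseline characteristic that predicts bone loss can be used in the design, by stratifying, or in the analysis, by adjusting. The plan states neither. Variation that such a characteristic explains therefore stays in the error term, and a chance difference between arms stays in the estimate.

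At stake is power for the 0.5 mm target and the width of the confidence interval. There is a second, smaller issue. If no covariate is named beforehand, any adjusted result reported later will have been chosen with the data in view.

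**Working it through.** **1. The plan's own figure.** Inputs from Statistical Considerations: "minimum clinically significant difference in bone loss of 0.5 mm", alpha 0.05, power 80%, "the number of patients will also be increased by 10% for each arm", and a minimum that "is 17 with for the test group (GS) and 17 for the control group (GL"). The text says "On the basis of this data, the minimum needed number of patients" follows, but no SD is given, so 17 cannot be reproduced. It can be solved backwards:
- 15 evaluable per arm becomes 17 either way: 15/0.9 = 16.7, or 15 × 1.1 = 16.5, both rounded up.
- With 15 per arm, two-sided 5% and 80% power, the implied SD is 0.472 mm by the t-test. By the normal approximation it is 0.5/[√(2/15) × 2.80] = 0.489 mm.

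I use 0.47 mm as an assumption. For the upper end of enrolment I take 25 per arm less 10%, so 22 evaluable.

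**2. Unadjusted power.** The calculation treats the primary test as a two-sample comparison of bone loss at one time point, which is a simplification because the plan names no primary contrast. Noncentrality = 0.5/[0.47 × √(2/15)] = 2.913, with 28 df and critical t 2.048. Power is 80.3%. With 22 per arm it is 93.1%.

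**3. Adjusted power.** With k covariates that together explain a share R² of the variance in bone loss, multiply the noncentrality by √{[(2n−2−k)/(2n−2)]/(1−R²)} and use 2n−2−k df. The first factor is the small-sample cost of chance imbalance in the covariates. Example with n = 15, k = 1, R² = 0.2: 2.913 × √[(27/28)/0.8] = 3.199 on 27 df, power 86.9%.

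| Evaluable per arm | Covariates | Unadjusted | R² = 0 | 0.1 | 0.2 | 0.3 |
|---|---|---|---|---|---|---|
| 15 | 1 | 80% | 79% | 83% | 87% | 91% |
| 15 | 2 | 80% | 77% | 81% | 86% | 90% |
| 22 | 1 | 93% | 93% | 95% | 97% | 98% |
| 22 | 2 | 93% | 92% | 94% | 96% | 98% |

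At 15 per arm, useless covariates cost 80.3 − 78.8 = 1.5 points with one and 80.3 − 77.1 = 3.2 points with two. Break-even R² is about 4% with one and 8% with two. Five covariates that explain 20% between them give 81%, so adding everything recorded gains almost nothing. With SD 0.489 mm the levels fall (77% unadjusted, 84% with one covariate at R² = 0.2), but the gain is still about 7 points.

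**4. Size of chance imbalance.** The shift in the estimated difference from imbalance in covariates explaining R² has standard error √R² × 0.47 × √(2/n). At 15 per arm this is 0.054 mm for R² = 0.1 and 0.094 mm for R² = 0.3, so 95% ranges of ±0.11 and ±0.18 mm.

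**5. Which recorded values qualify.**
- Cigarettes/day and CBCT bone height are obtained before allocation is revealed, so they cannot depend on arm.
- V2 MBL is the distance from the implant shoulder to bone. It exists only once the implant is in, after concealment is broken and after the arms have had different site preparation.
- Bone type during site preparation, ISQ and crown-implant ratio also arise after allocation and may depend on arm.

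**The case against.** The strongest objection is that no loss of precision has been shown. The documents give neither an SD nor any R² for bone loss. Smoking is capped at 10 cigarettes/day, which narrows its range. Below about 4% explained variance with one covariate, or 8% with two, adjustment costs power at 15 per arm. At 22 per arm the change is a few points on 93%. All of this stands, and it makes the gain conditional.

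A reader might infer four stronger points, which the documents do not support:
- **That the analysis uses no baseline information.** V2 MBL is the first repeated measure and the starting point of bone loss. Only its use as a covariate is absent.
- **That chance imbalance could be large against 0.5 mm.** Step 4 gives standard errors of 0.05 to 0.09 mm, and the unadjusted test already allows for this variation.
- **That the limits on smoking and bone height show the plan regards them as prognostic.** The Participants section gives no reason. The height range could equally reflect feasibility, since one arm receives a 5 mm implant without sinus lift and the other a 10 mm implant with it.
- **That V2 MBL is the natural covariate.** It is measured after allocation and could depend on arm. Bone up to the collar margin scores zero, so it may also vary little. If the outcome is change from V2, it has already been subtracted.

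The objection leaves the main fact untouched: suitable pre-allocation values are obtained, and the plan gives them no role.

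**Conclusion.** The point holds as an optional improvement in efficiency. No baseline value is named as a covariate and no stratification is stated, although cigarettes/day and CBCT bone height are available before allocation. A reader might take this as a bias in the primary result. It is not: the unadjusted randomised comparison remains unbiased.

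At 15 evaluable per arm, one covariate is worth roughly 2.5 to 10.5 points of power if it explains 10% to 30% of the variance (80.3% to 82.8–90.9%), and costs about 1.5 points if it explains nothing. These figures rest on an SD back-solved from the stated sample size, a two-sided test, a single-time-point comparison and an assumed R². The missing SD, primary time point and primary contrast are larger gaps and come first.

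**What to change.** State the primary time point first. Then prespecify in Statistical Considerations:
- The primary model is an ANCOVA or mixed model for bone loss, defined as the change in MBL from V2 to that time point. It contains arm and one, at most two, covariates fixed before allocation: cigarettes/day and, if wanted, CBCT residual bone height.
- The unadjusted difference is reported as a sensitivity analysis.
- V2 MBL serves as the starting point of bone loss. If it is also entered as a covariate, say that it is measured after allocation and show the result without it.
- Bone type, ISQ and crown-implant ratio are not used for adjustment of the primary comparison.

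The cost is a few sentences. No new measurement is needed, provided the CBCT height is kept as a number and not only as an eligibility tick. The statistical downside is the loss of about 1.5 points of power with one covariate, or 3 with two, if they prove unrelated to bone loss.

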#### **Prosthetic placement**

After 4 months of submerged healing, exposure of the implant and placement of a healing abutment is performed. After 2 weeks, the sutures are removed. After 5 months of submerged healing, impressions via pick-up impression copings are taken either using a polyether material (Impregum 3M/ESPE, Neuss, Germany) and/or a digital scan (TRIOS, 3Shape, Denmark). Within 1 to 3 weeks, definitive screw-retained metal-ceramic or metal-resin restorations are delivered.

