## **Patient Evaluation of Implant Treatment**

Please answer the following five questions. Place an "X" on the line indicating your satisfaction from 0 "not satisfied at all" to 100 "fully satisfied".

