## 1. DOES MY IMPLANT-SUPPORTED RESTORATION(S) FUNCTION WELL?

#### 2. DO I FEEL SECURE BITING/CHEWING ON MY IMPLANT-SUPPORTED RESTORATION?

#### 3. AM I PLEASED WITH THE ESTHETIC RESULT?

# 4. CAN I CLEAN MY IMPLANT-SUPPORTED RESTORATION(S) WELL?

#### 5. AM I SATISFIED WITH THE TREATMENT?

# 6. WOULD I UNDERGO THIS TREATMENT AGAIN, IF REQUESTED?

Extremely unlikely

Extremely likely

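### At 2 weeks the satisfaction form asks about a restoration that is delivered about 5 months later, so its items 1 to 4 cannot be validly answered at that visit

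*Combined protocol and SAP*

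**What the plan says.** Several sections place patient satisfaction at the 2-week visit.

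- Demographic data and patient questionnaires: "all patients will be asked at the 2-weeks, 12-month, and 24-month follow-up to give their perception of the received therapy", by means of a "questionnaire concerning function, esthetics, cleaning of the implant-supported restorations, satisfaction, and cost (Appendix C").
- Clinical measurement to monitor early healing: "patient satisfaction (Appendix B) will also be collected at the 2-week post-op visit".
- Follow-up evaluation visits lists satisfaction at 2 weeks and at 6 and 18 months after crown placement. In the Appendix A schedule, the row "Patient satisfaction" is marked at V3, V8 and V10.

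The section Prosthetic placement sets the timing of the restoration: "After 4 months of submerged healing, exposure of the implant and placement of a healing abutment is performed". Impressions follow at 5 months, and 1 to 3 weeks later "definitive screw-retained metal-ceramic or metal-resin restorations are delivered".

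Appendix C opens with "Please answer the following five questions", to be marked on a 0 to 100 satisfaction line, and then prints seven items. Item 1 reads "DOES MY IMPLANT-SUPPORTED RESTORATION(S) FUNCTION WELL".

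Patient satisfaction is secondary endpoint 7. Statistical Considerations plans a repeated-measures ANOVA for change over time and for group differences. It does not name the questionnaire or say which visits enter the model.

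**The concern.** At V3 the patient has a closed surgical site and no crown. Questions about how the restoration works, how secure chewing on it feels, how it looks and how easily it is cleaned then have no object.

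Two things can happen. The patient may mark the line anyway, and the mark measures something other than what the item states. It may well reflect the recent operation, which differs by arm because only the GL group has a sinus lift. That is an inference, but it means the error need not be equal between the groups. Alternatively, the item is coded not applicable, and there is no value at V3.

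What is at stake is how one secondary endpoint is read at its first time point, and any analysis of change that starts from that point.

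**Working it through.** No sample-size or power formula is involved. The check is a timeline and an item count.

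**Timeline**, in months after implant surgery, with 1 month = 30.44 days, so 1 week = 7 / 30.44 = 0.23 months.

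1. Crown, from Prosthetic placement: 5 months plus 1, 2 or 3 weeks = 5.23, 5.46 or 5.69 months. The middle value reproduces the 5 months and 2 weeks given under Follow-up evaluation visits.
2. First questionnaire (V3): 2 weeks = 0.46 months.
3. Gap from form to crown: 5.23 − 0.46 = 4.77 months at the shortest and 5.69 − 0.46 = 5.23 months at the longest.
4. Visit windows: take the impression 1 month early (4 months), delivery 1 week later, and V3 at its latest (16 days = 0.53 months). The gap is 4 + 0.23 − 0.53 = 3.70 months. No combination of windows brings the crown near V3.
5. Later questionnaires: 5.46 + 6 = 11.46 months (V8) and 5.46 + 18 = 23.46 months (V10). Both follow the crown.

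**Could anything else be rated at V3?** No provisional crown is described, and Post-surgical instructions tells patients not to wear a removable prosthesis during healing.

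**Items in Appendix C**

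| Item | Topic | Names the restoration? | Answerable at V3? |
|---|---|---|---|
| 1 | Function | Yes | No |
| 2 | Biting and chewing | Yes | No |
| 3 | Esthetic result | No | Not in substance; there is no prosthetic result yet |
| 4 | Cleaning | Yes | No |
| 5 | Satisfaction with treatment | No | Yes, about the surgery |
| 6 | Would undergo it again | No | Yes, about the surgery |
| 7 | Would recommend it | No | Yes, about the surgery |

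By wording alone 3/7 = 43% of items are tied to the restoration. With item 3 it is 4/7 = 57%. Either way this affects 1 of 3 time points, for all patients in both arms.

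**Does another section resolve it?** None limits the V3 form to certain items or supplies an early version. Clinical measurement to monitor early healing cites Appendix B for satisfaction, but Appendix B holds only pain scales. The same sentence cites Appendix A for the pain scale, and Appendix A is the visit schedule. Both labels are therefore one letter off, and no second instrument is implied.

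**Effect on the analysis.** If items 1 to 4 are coded not applicable at V3, and if a classical repeated-measures ANOVA were run on them over all three visits, no patient would have complete data. Both conditions are needed.

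**The case against.** The strongest reply is that the harm is small and partly hypothetical. The documents define no total satisfaction score. Statistical Considerations speaks of parameters in general and never says that the questionnaire enters a three-visit model. Data Management already provides a code for values that do not apply. If items 1 to 4 are so coded at V3, what remains is V8 and V10, where the form fits. Item 5, which asks about satisfaction directly, can be answered at 2 weeks.

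Most of this stands, and it sets the limits of the point. A reader might infer that the whole first satisfaction assessment is invalid, or that endpoint 7 is compromised. The documents do not support that: three items can be answered at V3, no total depends on the other four, and the later group comparisons are intact.

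A reader might also take the count of five in the Appendix C instruction for an error, since seven items follow. That does not hold either. Items 1 to 5 fit the satisfaction line that the instruction describes, whereas items 6 and 7 carry their own printed anchors of likelihood. Changing the count to seven would place those two items under a scale that contradicts their anchors.

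Two things survive the reply. The not-applicable code records a blank, but it neither stops patients from being asked nor prevents them from marking the line. And the ANOVA text makes no exception for V3.

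**Conclusion.** The point holds within those limits. As scheduled, items 1, 2 and 4, and in substance item 3, cannot be validly answered at V3, because the form precedes the crown by about 5 months (4.8 to 5.2 as planned, and at least about 3.7 with the windows). Items 5 to 7 are usable at V3 as an early measure of the surgical experience. They are not like for like with V8 and V10, where they refer to the completed treatment.

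This rests on two assumptions: that no provisional restoration is worn at 2 weeks, since none is described, and that the esthetic item refers to the prosthetic result. Without the second, the count falls from 4 to 3 of 7 items and the conclusion is the same.

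The matter is minor: one of eight secondary endpoints, at one early visit. The primary endpoint is unaffected. Separately, the protocol text says that the form covers cost, and Appendix C has no such item.

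**What to change.** 1. At V3, give only items 5 to 7. Compare them between the groups at that visit as a separate early measure.
2. Collect items 1 to 4 at V8 and V10 only.
3. State in Statistical Considerations that any repeated-measures analysis of satisfaction uses V8 and V10 only, for items 5 to 7 as well.
4. Reconcile the mention of cost in Demographic data and patient questionnaires with Appendix C, by adding an item or deleting the word.
5. Keep the count of five in the Appendix C instruction. If it is clarified, say that items 1 to 5 use the 0 to 100 satisfaction line and items 6 and 7 the likelihood line.

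The cost is a shorter form at one visit and a few wording edits. No visits or patients are added, and patients have less to fill in, unless a cost item is added.
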